##### **Effects**

The effects for the cost-effectiveness analysis will be Quality-adjusted life years (QALYs). QALYs were selected because of their ability to capture both morbidity and mortality domains of health and they are used across existing literature. The calculation of QALYs will be based on a patient's time spent in a specific health state multiplied by the utility weight for that respective of the state. Utility weights will be derived from published literature. For the 12-month analysis horizon, the time spent in each health state will be estimated using trial data. For the lifetime analysis horizon, a utility weight will be assigned to each health state and the running of the Markov model will provide the time spent for a hypothetical patient in each health state over their lifetime.

### Analysis

The model will estimate incremental cost-effectiveness ratios (ICER) between the dDPP and hDPP interventions. The results will be compared to standard willingness-to-pay thresholds for similarly-scaled public health programs in the US. Cost-effectiveness will be determined if the incremental cost-effectiveness ratio (ICER) is below the willingness-to-pay threshold. Both univariate and probabilistic sensitivity analyses will be performed varying key transition, utility, and cost parameters. The results from a probabilistic sensitivity analysis will be used to construct a cost effectiveness acceptability curve.

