### 3.1.7 COST-EFFECTIVENESS

This study seeks to evaluate the cost-effectiveness of a fully-automated intervention for diabetes prevention that does not require any human support outside of the maintenance and support of the app itself compared to a standard of care control group consisting of a human coach-based diabetes prevention program (hDPP) delivered via in-person or via distance learning modalities.

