Considering the low rates of referral and retention in the hDPP, a 15% difference in the primary endpoint would be considered acceptable in our clinical judgment in order to gain the advantages of a cheaper and scalable alternative to the current available intervention. In addition, there is significant variability in outcomes attained in real-world DPPs to justify this equivalence margin. Among a subset of hDPPs participating in our study (N=5), the proportion of completers achieving the 5% weight loss outcome was 50% (range 47% to 60%) and the 4% weight loss and 150 minutes of PA outcome was 50% (range 29% to 80%) (unpublished data). Of note, however, the outcomes reported by hDPP are calculated based on program completers (per protocol analysis). In our trial, we plan on conducting an intent-to-treat analysis. Thus, we expect that the observed  $\pi_s$  will be closer to the 30-40% range based on participant-level data across the U.S. from the CDC's national DPP.

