##### **Markov Model**

For the lifetime horizon analysis, we will construct a Markov model to simulate hypothetical patients exposed to either a dDPP or hDPP. The model will consist of health states reflective of prediabetes and diabetes such as normal glucose tolerance, impaired fasting glucose, impaired glucose tolerance, type 2 diabetes mellitus, and death. The transition probabilities between these health states will be calculated using data from the trial and published literature as needed. Again, given the relatively short duration of this trial, we do not expect a significant number of participants to convert from prediabetes to overt diabetes. Rather, we will estimate future diabetes incidence based on change in A1C as a proxy based on previously published studies. Life table estimates from the Centers for Disease Control and Prevention will be used to determine probabilities of death in all health states.

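### Section 9.4.9 calls dDPP cost-effective when the ICER is below the threshold; compared with hDPP, that reverses the net-benefit verdict whenever dDPP yields fewer QALYs

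*Combined protocol and SAP*

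**What the plan says.** Cost-effectiveness is in the trial's title and is listed among the secondary objectives and endpoints (Sections 1.1 and 3.3). Section 3.1.7 sets the direction: "This study seeks to evaluate the cost-effectiveness of a fully-automated intervention for diabetes prevention", with the human-coached programme as the standard-of-care control.

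Section 9.4.9 measures effects in QALYs over 12 months and over a lifetime. For the lifetime model, "we will estimate future diabetes incidence based on change in A1C as a proxy based on previously published studies". Under its Analysis heading it says: "The model will estimate incremental cost-effectiveness ratios (ICER) between the dDPP and hDPP interventions". It then says: "The results will be compared to standard willingness-to-pay thresholds for similarly-scaled public health programs in the US". No threshold figure is given. The decision rule follows: "Cost-effectiveness will be determined if the incremental cost-effectiveness ratio (ICER) is below the willingness-to-pay threshold". One-way and probabilistic sensitivity analyses and an acceptability curve are also planned, but the section does not say how a draw is classified for the curve. It contains no net-benefit criterion, no rule for dominance, and no separate reading for a less effective programme.

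Section 9.1 justifies the 15-point non-inferiority margin by saying that a shortfall of that size "would be considered acceptable in our clinical judgment in order to gain the advantages of a cheaper and scalable alternative to the current available intervention".

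**The concern.** A low ICER is good news only when the evaluated programme adds QALYs, because the ratio is then the price paid per QALY gained. When the programme is cheaper and less effective, the same ratio is the money saved per QALY given up, and a low value means a poor exchange. When the programme is dearer and less effective, the ratio is negative and therefore below every positive threshold.

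The rule makes no distinction between these cases. Followed as written for dDPP against hDPP, it could label a less effective app cost-effective when it loses net health benefit, or reject it when it gains. Because the criterion is prespecified, a correct verdict would depend on the analyst departing from it after seeing the sign of the QALY difference.

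**Working it through.** **Notation.** ΔC and ΔE are the cost and QALY differences, dDPP minus hDPP (direction from Section 3.1.7). L is the willingness-to-pay threshold. ICER = ΔC/ΔE. Net monetary benefit NMB = L·ΔE − ΔC; dDPP is worth adopting at L when NMB > 0.

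**Algebra.**
- ΔE > 0: ΔC/ΔE < L is the same as ΔC < L·ΔE, so NMB > 0. The rule is right.
- ΔE < 0: multiplying by a negative number turns the inequality round. ΔC/ΔE < L becomes ΔC > L·ΔE, so NMB < 0. The rule says yes exactly when net benefit says no, and the reverse, apart from the tie ICER = L.
- ΔE = 0: the ICER is undefined, but NMB is not.

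**Illustrations.** Section 9.4.9 gives no threshold, cost difference or QALY difference, so all dollar and QALY values here are assumptions. The threshold is varied over $50,000, $100,000 and $150,000 per QALY. The cases come in pairs with the same ICER.

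| Case | ΔC ($) | ΔE | ICER ($) | NMB at 50,000 | NMB at 100,000 | NMB at 150,000 | Stated rule | Net benefit |
|---|---|---|---|---|---|---|---|---|
| A | +300 | +0.01 | 30,000 | +200 | +700 | +1,200 | yes | yes |
| B | −300 | −0.01 | 30,000 | −200 | −700 | −1,200 | yes | **no** |
| C | +300 | +0.001 | 300,000 | −250 | −200 | −150 | no | no |
| D | −300 | −0.001 | 300,000 | +250 | +200 | +150 | no | **yes** |
| E (dDPP dominates) | −300 | +0.01 | −30,000 | +800 | +1,300 | +1,800 | yes | yes |
| F (dDPP dominated) | +300 | −0.01 | −30,000 | −800 | −1,300 | −1,800 | yes | **no** |

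For case B at $100,000: 100,000 × (−0.01) − (−300) = −1,000 + 300 = −700. Each pair shares one ratio and has opposite net benefit, so the ratio alone cannot carry the verdict.

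**Numerical check.** With 400,000 random pairs at each of the three thresholds (ΔE between −0.1 and 0.1, ΔC between −$10,000 and $10,000), the rule agreed with net benefit in 100% of pairs with ΔE > 0 and in 0% with ΔE < 0, whether dDPP was cheaper or dearer.

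**Is a less effective dDPP realistic?** Section 9.4.9 states no figure to reproduce, but the Section 9.2 sample size can be. With 50% success in both arms, a 15-point margin, one-sided 5% and 80% power, n = (1.645 + 0.842)² × 2 × 0.25 / 0.15² = 137.4, so 138 per arm; 138/0.75 = 184 after attrition. Both match the plan.

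With 138 per arm the standard error is √(0.5/138) = 0.0602, so an observed deficit up to 0.15 − 1.645 × 0.0602 = 0.051 still passes. If the true rates are equal at 50%, the chance of passing while the observed success rate favours hDPP is 0.5 − Φ(−0.051/0.0602) ≈ 0.30. At success rates of 40% and 30% it is about 0.32 and 0.36. These probabilities concern the 12-month composite, not QALYs.

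Costs can move the same way. Section 9.4.9 prices hDPP from the Medicare fee schedule. In the Section 5.6.2.2 table, a participant who attends both maintenance intervals and reaches 5% weight loss generates 2 × ($63 − $15) + $168 = $264 more than one with the same attendance and no such loss. Better hDPP results therefore tend to raise hDPP cost.

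**The case against.** The best counter-argument is that no reference arm is named. The ICER is described only as lying between the two programmes, and the secondary objective in Section 1.1 and the opening of Section 9.4.9 treat the two symmetrically. Swapping the order leaves the ratio unchanged and changes only which programme the verdict is about. If the verdict always concerned the more effective programme, the rule would be correct: in case B it would say that hDPP is worth its extra cost. This stands as a limit on the claim, and a reader should not infer that the rule fails under every convention. But that convention is not written, and Section 3.1.7 points to dDPP against hDPP.

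A second argument is that an acceptability curve is normally built from net benefit, and that an experienced health economist would handle dominance correctly. That may be so. The plan does not say it, and the only verdict it does define uses the ratio. Equally, the text does not show that the curve will be built wrongly.

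Two stronger readings are tempting. A reader might infer that the trial is designed to accept a QALY loss. The 15-point margin is on a binary 12-month composite that can be met on weight alone, while lifetime QALYs run through change in A1C. Section 9.1 also assumes equal success, and Section 2.2 suggests that dDPP may prove superior. A lower success rate makes fewer QALYs plausible, not certain.

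A reader might also infer that, if the programmes are truly equal, about half of the probabilistic draws would be misclassified. One half would describe estimates over repeated trials with symmetric error. Draws within one trial centre on that trial's estimate, and their negative share can be far from one half.

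**Conclusion.** Wrong as written. With dDPP compared against hDPP, the stated rule returns the reverse of the net-benefit verdict for every negative QALY difference, whatever the threshold and whatever the sign of the cost difference. This rests on algebra and on one assumption about direction, which Section 3.1.7 supports but Section 9.4.9 does not state. The dollar amounts are illustrations only; the documents do not allow the probability of a negative QALY difference to be calculated.

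The consequence is limited to a secondary endpoint. The primary analysis, the sample size and data collection are unaffected, and the verdict could be recomputed from the cost and QALY results the analysis already produces. It still merits correction, because this is a prespecified rule that can give the wrong answer in a plausible case, rather than a missing detail.

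**What to change.** Replace the decision sentence in Section 9.4.9 with:

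> dDPP is cost-effective versus hDPP if incremental net monetary benefit (threshold × QALY difference minus cost difference, dDPP minus hDPP) is positive at the stated threshold; dominance is reported as such, and any ICER is shown with its quadrant.

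Add that the acceptability curve plots, at each threshold, the share of probabilistic draws with positive net benefit. Since the section names no threshold, enter the figure or figures to be used before the analysis.

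The cost is one replaced sentence, one added sentence and a threshold value. No new data or modelling are needed, because net benefit uses the costs and QALYs already planned.

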#### 9.4.10 SAFETY ANALYSES

Safety analyses will be performed on the ITT population. Summary tables (frequency tables) will be provided for safety variables.

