## 8.3 SAFETY AND OTHER ASSESSMENTS

Since this study is focused on lifestyle modification (physical activity, healthy nutrition, and weight management) for diabetes prevention, it is considered to be a low-risk study with no obvious safety concerns. Participants will be informed of their laboratory results, height, and weight measurements at the study visit.

Participants' individual electronic medical records will be reviewed during screening and assessment of adverse events. Health Insurance Portability and Accountability Act (HIPAA) rules, other relevant federal or state laws, and local institutional requirements should be followed, as applicable.

A brief AE evaluation will be conducted (Section 11.20) at the 6 month and 12 month study visits.

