#### 8.4.4 TIME PERIOD AND FREQUENCY FOR EVENT ASSESSMENT AND FOLLOW-UP

The occurrence of an AE or SAE may come to the attention of study personnel during study visits and interviews of a study subject presenting for medical care, or upon review by a study monitor. All AEs including local and systemic reactions not meeting the criteria for SAEs will be captured on the appropriate CRF. Information to be collected includes event description, time of onset, clinician’s assessment of severity, relationship to study intervention (assessed by clinician), and time of resolution/stabilization of the event. All AEs occurring while on study must be documented appropriately regardless of relationship. All AEs will be followed to adequate resolution.

Any medical condition that is present at the time the subject is screened will be considered as baseline and not reported as an AE. However, if the study subject’s condition deteriorates at any time during the study, it will be recorded as an AE. UPs will be recorded in the data collection system throughout the study.

Changes in the severity of an AE will be documented to allow an assessment of the duration of the event at each level of severity to be performed. AEs characterized as intermittent require documentation of onset and duration of each episode.

The PI will record all reportable events with start dates occurring at any time after informed consent is obtained until 7 (for non-serious AEs) or 30 days (for SAEs) after the last day of study participation. At each study visit, the RC will inquire about the occurrence of AEs/SAEs since the last visit. Events will be followed for outcome information until resolution or stabilization.

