#### 8.4.5 ADVERSE EVENT REPORTING

AEs will likely be reported first to research coordinators during scheduled study visits or during follow-up communications and will be documented in the participant’s electronic case report form.

Research Coordinators are expected to enter adverse event information immediately into REDCap. The Research Coordinator will report the date of onset and resolution of the AE, description of the problem, adverse event preferred term using the MedDRA medical terminology, and the perceived grade of the AE. The Research Coordinator will contact the PI and Project Manager immediately by phone or text message for any perceived Grade 4 or higher AE (life-threatening consequences; urgent intervention indicated, or death related to adverse event). For all AEs entered into REDCap, the PI and project manager will immediately receive an email notification indicating that an adverse event has been reported, prompting further AE assessment. The PI will review the event and determine the grade, relatedness, and adverse event preferred term using the MedDRA medical terminology. If the lead PI ([name]) is not available, the research coordinator will contact the co-investigator ([name]) who will serve as a back-up.

The PI will record all reportable events with start dates occurring at any time after informed consent is obtained until 7 days (Grades 1-2) or 30 days (Grades 3-5) after the last day of study participation. At each study visit, the research coordinator will inquire about the occurrence of AEs since the last visit. Events will be followed for outcome information until resolution or stabilization.

The PI will inform the IRB, DSMB, and NIH program officer immediately when five grade 3 AEs are determined to be “probably related” to the study intervention. The DSMB will convene an ad hoc meeting by teleconference or in writing as soon as possible.

The DSMB will provide recommendations to the study team and sponsor (NIH). If the NIH determines that an unanticipated intervention effect presents an unreasonable risk to subjects, investigations, or parts of investigations presenting that risk will be terminated as soon as possible.

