## 9.2 SAMPLE SIZE DETERMINATION

Under a 1:1 randomization design, with a significance level (alpha) of 5% and 80% power, and assuming 50% of the participants achieve the primary outcome in both arms, 138 participants are required to enroll in each of the two arms, for a total study sample size of  $n = 276$ . Assuming a conservative attrition rate of 25% at 12 months, the adjusted sample size is set to 184 per group (368 total) to ensure the minimal necessary analyzable sample of 276 is retained. If there is truly no difference between the hDPP and dDPP, then 276 participants are required to be 80% sure that the upper limit of a one-sided 95% confidence interval will exclude a difference in favor of the hDPP of more than 15%. While it was previously noted that  $\pi_s$  will be closer to the 30-40% range, we used 50% in the non-inferiority sample size calculations as this choice yields the largest necessary sample size among all choices for  $\pi_s$ , and thus makes the study robust, in terms of statistical power, to other values for  $\pi_s$ .

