## 9.3 POPULATIONS FOR ANALYSES

Consistent with the **intention-to-treat (ITT)** principle, results of all study participants will be evaluated according to initial randomization regardless of whether they adhered to their assigned treatment and regardless of protocol violations or deviations. Analyses of effectiveness endpoints, however, will exclude participants who withdraw from the study or withdraw consent. Effectiveness analyses will be performed for the ITT population. All primary statistical analyses of effectiveness measures will be unadjusted and two-sided tests of significance will be used. A per-protocol analysis will also be conducted using the population of program completers in each group, as defined in Section 3.3, to benchmark outcomes against CDC standards.

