## 11.21 ADVERSE EVENT EVALUATION

Have you had any new medical problems since the last visit?	 Yes. Please describe the new medical problem(s).  No
Do you think the medical problem(s) was related to your [use of the Sweetch digital diabetes prevention program/ participation in the DPP]	 Yes. If Yes, Why do you believe the medical problem(s) was related to the [Sweetch DPP/ DPP]?  No

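### Adverse events are tabulated on all randomised participants but asked about only at months 6 and 12, so planned attrition can understate AE percentages and, if it differs by arm, flatter the arm with more loss

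*Combined protocol and SAP*

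**What the plan says.** Section 9.4.10 is short: "Safety analyses will be performed on the ITT population. Summary tables (frequency tables) will be provided for safety variables". It gives no denominator for percentages, no follow-up time, no number assessed, and no handling of participants without an AE assessment.

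The ITT population in Section 9.3 is everyone as randomised. The one exclusion there is confined to effectiveness: "Analyses of effectiveness endpoints, however, will exclude participants who withdraw from the study or withdraw consent". Section 7.3 classes participants lost to follow-up as withdrawn, so they leave the effectiveness analyses but stay in the safety tables.

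On collection, Section 8.3 states: "A brief AE evaluation will be conducted (Section 11.20) at the 6 month and 12 month study visits". The Schedule of Activities (Section 1.3) marks the same two visits. Section 8.4.4 adds: "At each study visit, the RC will inquire about the occurrence of AEs/SAEs since the last visit". The form asks: "Have you had any new medical problems since the last visit". (The form is in Section 11.21; the Schedule points to 11.19 and Section 8.3 to 11.20. These references should be aligned.)

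Other routes are described. Section 8.4.5 says "AEs will likely be reported first to research coordinators during scheduled study visits or during follow-up communications"; Section 8.3 says that "individual electronic medical records will be reviewed during screening and assessment of adverse events"; and Section 8.4.4 mentions participants presenting for care and review by a monitor. None of these is scheduled for participants who miss visits.

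Section 9.2 sets the expected loss: "Assuming a conservative attrition rate of 25% at 12 months". It is one overall rate, with no split by arm.

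**The concern.** A frequency table on all randomised participants treats everyone as equally observed. Here they would not be. Someone lost before month 6 has had no scheduled AE enquiry, and someone lost between months 6 and 12 has had half the year covered. Each adds one to the denominator; an event in the uncovered time adds to the numerator only if another route finds it.

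The first consequence is that AE percentages, including those for the musculoskeletal events that Section 8.4.3.3 expects, may be too low in both arms. The second is conditional: if the app arm and the class arm lose participants at different rates, the arm with more loss could look safer with no difference in true risk. No between-arm safety test is planned, but the DSMB reviews safety by arm (Section 10.1.8), so the two columns will be read side by side. Section 9.4.12 rules out listings of individual data by measure and time point, so readers of the results may be unable to reconstruct who was assessed.

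**Working it through.** **Planned loss.** Section 9.2 uses 50% success in both arms, a 15-point margin, one-sided 5% and 80% power:

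n = (1.645 + 0.842)² × 2 × 0.5 × 0.5 / 0.15² ≈ 137.4, so 138 per arm. Then 138 / (1 − 0.25) = 184 per arm, 368 in total. Both stated figures reproduce. With 25% loss in each arm, 184 × 0.25 = 46 participants per arm could lack a 12-month AE evaluation.

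**Model.** The documents give no AE risk and no arm-specific attrition, so both are assumed here. Let r be the true 12-month risk of at least one AE, equal in both arms, with constant hazard. Let e be the share lost before month 6 and l the share lost after attending month 6. With no capture outside visits (worst case), the ITT percentage is

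(1 − e − l) × r + l × [1 − (1 − r)^0.5].

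For r = 20%, the half-year risk is 1 − √0.8 = 10.56%.

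**Equal loss of 25%, r = 20%.**
- All before month 6: 0.75 × 20% = 15.0%.
- Half before, half after: 15.0% + 0.125 × 10.56% = 16.3%.

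Both arms are understated and there is no false difference.

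**Unequal loss, 15% against 35% (mean 25%), r = 20%.**

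| When participants are lost | 15% lost | 35% lost | Gap (points) |
|---|---|---|---|
| All before month 6 | 17.0% | 13.0% | 4.0 |
| Half before, half after | 17.8% | 14.8% | 2.9 |
| All after month 6 | 18.6% | 16.7% | 1.9 |

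(Gaps are from unrounded values.)

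**Range for early loss.** The gap is r × (difference in loss).
- 15% against 35% loss: 2.0 points at r = 10%, 4.0 at 20%, and 6.0 at 30% (25.5% against 19.5%).
- At r = 20%: 2.0 points for 20% against 30% loss, and 6.0 for 10% against 40%.

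**Partial capture.** If other routes find a share c of the events in participants lost early, the gap becomes r × (difference in loss) × (1 − c). For 15% against 35% at r = 20%, c = 50% gives 20% × 20% × 0.5 = 2.0 points (18.5% against 16.5%).

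**Which denominator repairs what.** Dividing by participants with at least one completed AE evaluation:
- Early loss: 17.0 / 0.85 = 20.0% and 13.0 / 0.65 = 20.0%, on 156 and 120 participants. The true risk is restored.
- Split loss: 17.8 / 0.925 = 19.2% and 14.8 / 0.825 = 18.0%. Partly restored.
- Late loss: everyone has one evaluation, so the 18.6% against 16.7% is unchanged.

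The assessed denominator therefore does not deal with half-covered participants; person-time is needed for that. Under this model the first-event rate is −ln(0.8) = 0.223 per person-year in both arms, but that holds by construction and does not show that rates are unbiased when loss is related to AEs.

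**The case against.** A reader might infer that the plan counts participants who miss visits as event-free. No section says so. That outcome is the arithmetic of a table on all randomised participants, and it applies in full only to someone who misses both visits and is found by no other route. Enquiry covers the time since the last visit, so a missed month-6 visit can be recovered at month 12.

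A reader might also infer that unequal attrition will produce a false safety difference. The documents do not support that: 15% against 35% is an assumption, and equal loss produces no gap. Nor does leaving the programme mean leaving the study. Section 7.1 commits staff to keeping non-engagers in the study, with AEs named as a reason, and Sections 5.6.5 and 7.3 set out contact attempts and rescheduling. These procedures are the same in both arms.

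Zero capture is a worst case. Coordinators contact participants about monthly Actigraph wear and activity surveys, and Section 8.2.5 offers electronic follow-up questionnaires with telephone completion, though whether that covers the AE form is not stated.

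The worst-case gap is also modest. For 17.0% against 13.0% with 184 per arm, the standard error is √[(0.17 × 0.83 + 0.13 × 0.87) / 184] ≈ 3.7 points, so 4 points is about 1.1 standard errors, in tables that are descriptive only.

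All of this stands as a limit on size and certainty. It does not supply the missing denominator: the other contacts are not scheduled AE enquiries and may not reach participants who are truly lost.

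**Conclusion.** The point holds as a gap in the safety analysis. AE enquiry is scheduled only at months 6 and 12, the tables rest on all randomised participants, a quarter are expected to be lost, and nothing records how long or how completely each participant was observed. AE percentages may be understated: at an assumed 20% risk with no other capture, by up to 5 points at the planned attrition (15% shown). A between-arm artefact is possible, not established. It is 4 points for an assumed 15% against 35% early loss, smaller if loss comes later or other routes find events, and nil if loss is equal.

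It would also go too far to conclude that exposure-adjusted rates should replace the ITT counts. Rates that stop at the last completed evaluation could leave out a serious event found later, or one in a participant who was never evaluated. Both displays are needed.

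**What to change.** In Section 9.4.10:

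1. Keep the ITT counts by arm, and list every event, including those found outside visits or after the last evaluation.
2. Add, by arm, the number assessed for AEs at each of the two visits.
3. Add percentages among participants with at least one completed AE evaluation.
4. Add exposure-adjusted rates per person-year with a 95% CI, with person-time running from randomisation to the last completed AE evaluation. Limit the numerator to events inside that person-time and list the others separately.
5. State that any between-arm safety description draws on the ITT counts and the exposure-adjusted rates together, not on the rates alone.

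The cost is SAP wording and one extra table, using visit dates and AE onset dates that the protocol already collects (Sections 8.4.4 and 8.4.5). The rates assume a roughly constant hazard and loss unrelated to AEs, which should be stated beside them. The visit schedule and clinical management are unchanged.
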